**University of Florida IRB-01
Protocol**

Title: A sociolinguistic-enabled web application to develop precision health intervention for African Americans

Investigators: [name] (PI), [name], [name], [name], , [name], [name], [name]

1. Abstract:

This pilot study will explore the preliminary efficacy of a colorectal cancer (CRC) screening intervention delivered by virtual health assistants (VHAs). Participants will include 750 patients in the US between the ages of 45 and 75 recruited through Qualtrics panels: 375 who are non-adherent to CRC screening guidelines, and 375 patients who are adherent to CRC screening guidelines. The main research question is: How does the integration of different levels of dialect density of the linguistic features of African American English (AAE) influence the perceived credibility of a Black VHA? Four types of VHAs will be presented to our patients: a VHA with Standardized American English (SAE) linguistic features, a VHA with a low level of African American English (AAE) linguistic features integrated, a VHA with a high level of African American English (AAE) linguistic features integrated, and a text-only control condition. Survey questions will be used to obtain credibility judgments about VHAs post-interaction.

2. Background:

B.2. African American English. Over the last 60 years or so, a profusion of scientific inquiry performed mainly by African American linguists and scholars has provided a nuanced look into the mosaic of African American language use (Lanehart & Malik, 2015). The main goals of this linguistic endeavor were to dispel racist myths of linguistic deficiency, explicate the legitimate, systematic, and rule-governed nature of the linguistic varieties of many African Americans, and dismantle the linguistic discrimination and institutional racism which had produced disparate harm for speakers in realms such as education, job procurement, and healthcare (Baugh, 2018). For the purpose of this pilot study, three main aspects are relevant. First, researchers have identified specific pronunciation, sound, and grammatical structures from the speech of various groups of African Americans across the United States and throughout various time periods that do not appear in Standardized American English (SAE). Together, these structures, along with other linguistic features, have traditionally been termed African American English (AAE)¹ (Green, 2002). These linguistic features are not inferior or flawed versions of SAE counterparts, an idea that white supremacist narratives baked into U.S. society and the U.S. education system promote (Lippi-Green, 2012), but rather display the normal traits of all languages and linguistic varieties, play an important role in social interactions and identity building (King & Rosa, 2019), and are a part of the speech of 80-90% of African Americans at some level (Rickford, 1999; Smitherman, 1998). Second, AAE is not a delimiting set of structures that defines all African American speech. The speech of individual African Americans may or may not contain the linguistic features of AAE, along with SAE and also other language varieties. Third, the speech of individual African Americans is influenced not only by racialization but also by the intersections of various social identities (King & Rosa, 2019) such as gender, age/generation, education, sexuality, occupation, religion, ability status, social/socioeconomic class, and regional background (Alim & Reyes, 2011).² All of these layers contribute to larger linguistic repertoires that vary by individual and may be consciously or subconsciously drawn upon as African American speakers "shape and engage in processes and projects of identification" (Alim, 2016) in various contexts and social situations.

The speech of African Americans, then, is a mosaic, rather than a monolith. At the same time, however, Black linguists and scholars estimate that between 80-90% of the African American population retain and utilize a selection of the linguistic features of AAE at varying level as they weave through the various interactions in their lives (Smitherman, 1998; Rickford, 1999; Hutcheson, 2018). We find it plausible, therefore, that many of the participants in this study may utilize these features at some level as well and may find our VHA's linguistic accommodation appealing.

B.3. Linguistic accommodation. The connection between dialect density and cancer screening adherence has to do with trust and accommodation. Accommodating to a shared linguistic style improves communication effectiveness, understanding, and trust, which can lead to message compliance (Giles et al., 2007). Both objective and perceived language similarities enhance perception of credibility, competence, and persuasiveness (Aune & Kikuchi, 1993). In the clinical setting, healthcare providers who

¹ The term African American Vernacular English (AAVE), among others, has also widely been used.

² African American English is also not limited to the African American community but can be the first language of any person.

match their communication style to that of patients are considered most appropriate (Bourhis, Roth, & MacQueen, 1988). This is especially salient among racial ethnic minorities, who may maintain or accentuate linguistic features tied to racial identity in order to protect their racial identity (Bourhis & Giles, 1977, Giles & Johnson, 1987). For example, racial minorities might view “standard” language as more socially desirable but find the “non-standard” similar accent persuasive (Giles, 1973). Therefore, making an African American healthcare provider option with shared linguistic features is not cultural insensitivity, but rather a potential accommodation to those whose speech patterns also have non-standard linguistic features.

Accommodating to various African American patients’ speech is equivalent to communicating with patients competently, through appropriate (not offending others) and effective (meeting the goal) means (Cupach & Spitzberg, 1983). In communication, all humans navigate identity and solidarity with interlocutors through linguistic accommodation. If we feel connected to someone, we speak more like they do; if we don’t, we dissociate our speech from theirs. This has been shown to be true with doctor-patient interactions as well, particularly with African American doctors and patients using AAE (Tamasi, 2008; Wood, 2019). Our hope is to understand if the use of AAE by our virtual doctors increases trust and comfort with this screening process or not.

Previous research done by this team has shown a clear positive effect of racial identity via appearance on the response of patients of color. When patients of color were paired with a virtual health professional that matched their racial identity, patients were much more likely to follow-up with colorectal cancer screenings. Building off these findings, we plan to investigate whether the adjustment of linguistic features will have a positive, neutral, or negative effect.

3. Specific Aim:

African Americans are at risk for a number of health inequities, including increased morbidity and mortality due to colorectal cancer (CRC) as compared to White Americans. While the reasons for this inequity are complex, the disparity can be reduced through regular screening. Unfortunately, adherence to CRC screening guidelines is low, especially among African Americans. One strategy for reducing CRC screening disparities is to develop strategic communication interventions about the fecal immunochemical test (FIT), a low-cost, non-invasive screening method that alleviates common patient barriers to CRC screening and is equally effective as colonoscopy screening in reducing CRC incidence and mortality.

Interventions that use tailored messages are effective for improving CRC screening. However, two important questions must be answered before tailored screening interventions can be implemented in healthcare systems. One is the degree to which message content must be tailored to be effective and another is how to effectively engage participants. The current project is an extension of an existing project that uses mobile virtual human technology (VHT) to deliver tailored CRC screening messages for African Americans to improve screening within guidelines. Interventions using VHT offer numerous advantages, including the capability to be customized to the linguistic preferences of the patient. As such, the use of virtual technology could help reduce CRC screening barriers such as cultural mismatch and low self-efficacy among African American patients.

The purpose of this proposal is to investigate to what extent the incorporation of AAE linguistic features increases, decreases, or has no effect on the perceived credibility of VHAs. This pilot study is meant to be exploratory in nature. We seek to explore the following specific aim:

- Examine how tailoring the dialectal variety of the speech of VHAs influences their perceived credibility. **Approach:** Each participant will interact with a VHA that differs in speech containing

either: (1) strictly linguistic features of SAE, (2) a low level integration of AAE linguistic features, (3) a high level integration of AAE linguistic features, or (4) a voiceless, text-only control. Post-interaction, participants will be asked to judge how credible they felt the VHA was through survey questions.

4. Research Plan:

6.1. Pilot study design. This pilot study will use a posttest-only, 3 (SAE: Standardized American English / low level AAE: African American English / high level AAE) x 2 (Introduction / No introduction) with a control group (i.e., no voice) randomized experimental message design. Patients (N=750) will be recruited from a national panel by Qualtrics. In order to be included in the study, participants must be between the ages of 45-75, and have health insurance. We will recruit equal numbers of male and female patients.

After providing informed consent, participants will be randomly assigned to a VHA. Participants will be assigned at random to a Black, gender-matched VHA that speaks SAE, AAE (low level), or AAE (high level). Each VHA will also either include an introduction from the voice actor/actress or will not include an introduction. The control group will be the same intervention content delivered via text-only (e.g., photos of the Black VHA). After completing the intervention, participants will complete a questionnaire with dependent measures and potential mediators. This questionnaire will solicit participant opinion on the credibility of the VHA and also gauge the participant's intent to screen for CRC. Participants will receive monetary compensation which will be credited to their Qualtrics member account on the site.

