Descriptive statistics for credibility score including mean, standard deviation, median, and inter-quartile range (IQR) will be calculated (1) in the overall study cohort and (2) within each of the 7 groups. Similarly, descriptive statistics for intention to CRC screen including frequency and proportion will be calculated (1) in the overall study cohort and (2) within each of the 7 groups. Such information will serve as preliminary estimates to facilitate future powered studies. We will also generate descriptive statistics of collected demographic and clinical variables (e.g., age, gender, etc.). Graphical illustration will be provided if applicable. One-way ANOVA or Kruskal-Wallis test will be used to test difference of credibility score among 7 groups and two-sample t-test or Wilcoxon rank sum test will be used for post-hoc pairwise comparison. Chi-squared test or Fisher exact test will be used to test difference of intention to CRC screen among 7 groups and pairwise comparison. As this is a pilot study, all statistical analysis is exploratory. Therefore, multiple comparison adjustment will not be considered.

6.8. Patient-centeredness. The proposed intervention will test different levels of linguistic variation. To maximize patient centeredness, the investigators will conduct formative research with members of the intended patient population during the period in which the current study is under review at NCATS. The co-PI ([name]) currently has an open protocol in which focus groups are being used to ensure patient acceptability of all aspects of the VHAs. For more details on focus group procedures, please see our recent manuscript published in *Psycho-Oncology* (see [name] et al., 2020). [name] will conduct additional focus groups to examine patient perceptions of the different levels of linguistic variation and use this feedback to finalize how the stimuli are presented in the experiment to maximize patient centeredness.

5. Possible Discomforts and Risks:

- As with any behavioral intervention, there is the possibility of minimal emotional discomfort from being presented with individual risk factors for a disease. However, the probability of any physical, psychological, or social harm is minimal to none.

Adverse Event Reporting

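### Recruitment is set by screening adherence and sex, but no balancing of the seven arms on adherence is described and the analysis uses neither factor: the tests stay valid, at a modest cost in precision

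*Combined protocol and SAP*

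**What the plan says.** The abstract sets two halves by screening history: "375 who are non-adherent to CRC screening guidelines, and 375 patients who are adherent to CRC screening guidelines". This split appears only there. Section 6.1 gives the total ("Patients (N=750) will be recruited from a national panel by Qualtrics"), states eligibility as "participants must be between the ages of 45-75, and have health insurance" without mentioning adherence, and adds a second margin: "We will recruit equal numbers of male and female patients". No section crosses the two margins.

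The design in 6.1 is three speech types "x 2 (Introduction / No introduction) with a control group (i.e., no voice) randomized experimental message design", which makes seven arms. On assignment, 6.1 says "After providing informed consent, participants will be randomly assigned to a VHA" and "Participants will be assigned at random to a Black, gender-matched VHA that speaks SAE, AAE (low level), or AAE (high level". It gives no allocation ratio, blocking or stratification.

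Section 6.7 describes and tests credibility (the primary outcome) and intention to screen, summarising each "within each of the 7 groups". The tests are a one-way ANOVA or Kruskal-Wallis test for credibility, a chi-squared or Fisher test for intention, and the matching pairwise tests. None has an adherence or sex term, and no analysis by either factor is planned.

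**The concern.** The study must learn each person's screening history to fill the 375/375 quota, and each person's sex to choose the matching VHA. As written, adherence then plays no part in assignment, and neither factor enters the analysis. The balance achieved in the whole sample is not carried into the seven groups being compared.

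This matters because the design is posttest-only, so there is no baseline credibility or intention to adjust for. Adherence is the one likely prognostic variable that the plan already commits to collecting, and it plausibly relates to intention to screen. Section 6.7 says the group estimates are meant to inform later powered studies, and 6.7 also says the sample size is set by budget. Any extra precision therefore has to come from the allocation and the analysis.

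**Working it through.** The plan has no power or sample-size calculation to reproduce. Its arithmetic is consistent: 375 + 375 = 750, and 3 × 2 + 1 = 7 arms. Equal allocation is my assumption and gives 750 / 7 = 107.1 per arm.

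**1. Chance imbalance in adherence without stratification.** For two arms of 107 drawn from 375 adherent and 375 non-adherent people:

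- SD of the difference in adherent share = √[0.25 × (750/749) × (2/107)] = 0.068. Simulating 100,000 allocations gives 0.0687 with fixed arm sizes and 0.0685 with simple randomisation. A separate run of 20,000 simple randomisations gives 0.069.
- The chance that a given pair differs by about 10 points or more is 14% to 15%.
- Seven arms form 7 × 6 / 2 = 21 pairs. The largest gap among them averages about 13 points (95th percentile about 20), and reaches 10 points in about 77% of allocations.

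**2. Validity.** In 4,000 simulated null trials per scenario, the type I error of the unadjusted ANOVA was 4.5% to 5.2%. The assumptions were an adherence effect of 0.5 or 0.8 SD, a sex effect of 0.3 SD, and 50% or 80% of women adherent. The nominal level is kept.

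**3. Precision for intention.** Assume a yes/no intention averaging 50%, and a difference d between adherent and non-adherent people.

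- Share of variance explained by adherence = (d²/4) / 0.25 = d². For d = 0.10, 0.30 and 0.40 this is 1%, 9% and 16%.
- Unadjusted standard error of a pairwise difference = √(2 × 0.25 / 107) = 6.8 points.
- With adherence used, at d = 0.30: 6.84 × √(1 − 0.09) = 6.5 points. Over the range: 6.84 × √0.99 = 6.8 and 6.84 × √0.84 = 6.3 points.

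**4. Shift in a raw intention difference, at d = 0.30.**

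- Given pair: mean absolute gap = 6.87 × √(2/π) = 5.5 points, and 5.5 × 0.30 is about 1.6 points.
- Worst of 21 pairs: 13 × 0.30 = 3.9 points.
- Both are below one standard error (6.8 points).

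**5. Precision for credibility.** Assume a true difference of 0.4 SD, 107 per arm and two-sided 5%. Power = Φ(0.4 / [s√(2/107)] − 1.96), where s² = 1 + d²/4 if an adherence effect of d SD is left in the error.

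| Adherence effect left in | s² | Power |
|---|---|---|
| none (variance removed) | 1 | 83% |
| 0.5 SD | 1.0625 | 81% |
| 0.8 SD | 1.16 | 78% |

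**6. After the fix.** Take four adherence-by-sex strata of 187 or 188, allocated in blocks of 7. Each arm receives 26 or 27 people per stratum, hence 52 to 54 adherent and 52 to 54 non-adherent. The adherent share lies between 52/106 = 49.1% and 54/106 = 50.9%, so the largest gap is about 2 points.

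**The case against.** The other side has a strong case. This is a declared exploratory pilot, and unstratified randomisation of 750 people is legitimate. Ordinary standard errors already include chance imbalance. The gain is small and rests on assumed effects, and the documents give no reason to expect adherence to predict credibility, the primary outcome. All of this stands and limits the weight of the point. It does not remove it, because a variable that must be collected anyway goes unused.

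A reader might infer more than the documents support, in four ways:

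- **That the arm comparisons are biased.** They are not. Imbalance arises only by chance, and type I error stays near 5%.
- **That 13 points is the typical imbalance.** It is the average of the worst of 21 pairs. A given pair differs by about 5.5 points on average.
- **That the plan rules out stratification.** It is silent on method. Gender matching already brings sex into assignment, and a survey that branches on sex and randomises within each branch would fit the wording. Only balancing on adherence is wholly unmentioned.
- **That uncrossed quotas confound adherence with the VHA's gender and so damage the results.** The two margins do permit anything from 0 to 375 adherent women. But random assignment puts both sexes in every arm, so the dialect comparisons are unaffected, and 6.7 plans no comparison by sex, VHA gender or adherence. VHA gender is tied to participant sex by design, whatever the quotas. Short of a complete association, stratifying or adjusting would separate adherence from sex, and the documents do not suggest any association.

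**Conclusion.** The point holds as a modest loss of efficiency, not an error. The plan recruits by adherence and sex, describes no balancing of the arms on adherence, and analyses them without either factor. Its tests remain valid.

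The intention result depends on the assumed 30-point adherence difference: the reduction in standard error is about 0.3 points there, negligible at a 10-point difference and about 0.5 points at 40. The credibility result is 2 to 5 percentage points of power, and only if adherence shifts credibility by 0.5 to 0.8 SD. Equal arms of about 107, 50% average intention, a yes/no intention measure and the 5% level are also my assumptions, since the plan states none of them. The change is worth making because it costs almost nothing, and because even allocation cannot be added once people have been assigned.

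**What to change.** **Section 6.7.** Add adherence and sex as factors in the seven-group and pairwise comparisons: a linear model for credibility, and a logistic model or a stratified test for intention. For intention, also report a stratum-weighted difference in proportions. The gain in points calculated above applies to that scale, not to a log odds ratio. Keep the unadjusted tests alongside, and tabulate adherence and sex by arm.

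**Section 6.1.** State the allocation ratio and method. Ask the adherence and sex screener items before assignment, and allocate evenly to the seven arms within each adherence-by-sex stratum. If this is already intended, saying so settles that part. Bring the adherence quota from the abstract into 6.1.

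**Cost.** A small change to the survey flow, a few sentences in 6.1 and a short rewrite of 6.7, with no extra participants or measures. Crossing the recruitment quotas (187 or 188 per cell) is optional. It would help only a later look by adherence or sex, adds nothing to the dialect comparisons, and may slow the filling of the last cell.

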6.2. National panel recruitment information

According to Qualtrics' IRB Information Sheet, "Participants are recruited from various sources, including website intercept recruitment, member referrals, targeted email lists, gaming sites, customer loyalty web portals, permission-based networks, and social media, etc." With regards to how panel members are invited to a survey, "Panel members are sent an email invitation or prompted on the respective survey platform to proceed with a given survey. The typical survey invitation is generally very simple and generic. It provides a hyperlink which will take the respondent to the survey as well as mention the incentive offered." More information is available in the Qualtrics' IRB Information Sheet attached under Section 3.0 of the "Miscellaneous Attachments" page in the IRB smartform system.

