6.3. Informed consent process

The first page of the Qualtrics survey will display the information outlined in the informed consent form document. Specifically, the following passage will be included on this informed consent page, "Completion and return of the survey implies that you have read the information in this form and consent to take part in the research. Please keep this form for your records or future reference."

6.4. Timeline. The proposed pilot study is funded through the CTSI. As such, the study team is required to receive UF IRB approval prior to the procedures being submitted to NCATS for additional review. The additional review required by NCATS is expected to take two months. Thus, it is important for the study team to receive SRMC approval for the randomized message design experiment that was funded by the CTSI as soon as possible.

6.5. Stimuli. The speech of the VHA will be manipulated by varying its Dialect Density Measure (DDM) which is the number of dialectal features that are specific to AAE within an utterance in proportion to the number of words spoken in that given utterance. At the pronunciation level, this may include features such

as -g dropping, as in, "I'm gettin' a cold." At the grammatical level, this may include features such as the zero copula/auxiliary ("be" verb) as in, "How you feeling today?"

The scripts with different levels of dialectal density will be read by professional voice actors/actresses. Specific instructions and speech samples illustrating our target AAE features will be provided to the voice actors to ensure a natural and native production of AAE. The instructions will be designed by our team's linguists who have experience conducting linguistic fieldwork and communicating with laypeople without using technical terminologies.

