AAE linguistic features to be added will be drawn from linguistic literature and scholarly research (as outlined in Section B.2.). Further, to ensure that each feature is an authentic representation of AAE, the [Corpus of Regional African American Language \(CORAAL\)](#) (Kendall & Farrington, 2020) will be consulted on the particular feature in question to ascertain whether the feature actually appears in the speech of various African Americans. CORAAL is a corpus of over 150 hours of recordings of interviews with African Americans from around the country and over time. CORAAL is especially beneficial in this process as it contains the speech of African Americans who differ in gender, age, and regionality, and the recordings span the late 1960s to the late 2010s. As much as possible, actual audio snippets of African American speakers using the linguistic feature in question will be included in the script via hyperlink both as an accountability mechanism to ensure the scripts avoid incorrect, stereotyped language and also to offer voice actors/actresses real life examples of the features to assist them in producing the most authentic and natural voice recording possible.

6.6. Measures. The primary outcome in the current pilot study is credibility score. We expect that source credibility is the mechanism through which intentions to screen will be strengthened. Source credibility will be measured using a series of semantic differential items (e.g., "Please rate your virtual health assistant on the following dimensions": Trustworthy/Untrustworthy, Honest/Dishonest, Expert/Inexpert, Competent/Incompetent). Further, we will measure whether the integration of AAE linguistic features impacted credibility through the use of usability questions (e.g., "How would you describe your virtual health assistant on the following scales:" "Is similar to me/Is different from me", "Speaks like me/Does not speak like me"). Given that the primary manipulation in this study is speech characteristics associated with ethnic group membership, we will also assess strength of ethnic identity using the Multi-group Ethnic Identity Measure.³⁹

6.7. Sample size justification and statistical analysis plan. As this is a pilot study, our main purpose is preliminary information collection and exploratory analysis instead of hypothesis testing, a formal sample size calculation is not necessary. The study sample size is determined by budget.

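### The protocol describes no check that participants can hear audio, although the primary manipulation is recorded speech and only the six voiced groups need sound

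*Combined protocol and SAP*

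**What the plan says.** - **Eligibility (6.1).** "In order to be included in the study, participants must be between the ages of 45-75, and have health insurance". No hearing, device or sound requirement is listed.
- **Order of steps (6.1).** "After providing informed consent, participants will be randomly assigned to a VHA". Nothing is described between consent and allocation.
- **Voiced groups (6.1).** "Participants will be assigned at random to a Black, gender-matched VHA that speaks SAE, AAE (low level), or AAE (high level". Each of these three is given with or without an introduction from the voice actor, which makes six voiced groups.
- **Control (6.1).** "The control group will be the same intervention content delivered via text-only (e.g., photos of the Black VHA". This group needs no sound.
- **What is manipulated (6.5, 6.6).** "The scripts with different levels of dialectal density will be read by professional voice actors/actresses". The measures section confirms the emphasis: "Given that the primary manipulation in this study is speech characteristics associated with ethnic group membership".
- **Setting (6.2 and Adverse Event Reporting).** "Panel members are sent an email invitation or prompted on the respective survey platform to proceed with a given survey". The study team has no direct contact with participants.
- **Measures (6.6).** The nearest item asks, after the interaction, whether the assistant speaks like the respondent. It does not ask whether any speech was heard.
- **Analysis (6.7).** Seven groups are compared overall and pairwise. There is no rule for people who did not hear the recording or who did not finish.

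**The concern.** A participant in a voiced group whose sound is off or not working does not receive the spoken manipulation, but can still rate the assistant's credibility, which is the primary outcome. In the text group the same person loses nothing. Two different harms can follow, and they fall on different comparisons:

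- **Non-hearers who stay and answer.** Their ratings cannot differ by spoken dialect, so the differences between SAE, low AAE and high AAE shrink toward zero. The specific aim allows for no effect as a finding, and unheard audio pushes toward that finding without leaving a sign in the data.
- **Non-hearers who leave.** They leave the voiced groups, while their counterparts in the text group remain. The voiced-versus-text comparison is then between differently selected people. Section 6.3 ties consent to completing and returning the survey, so those who break off may leave no usable record from which to examine this.

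Recruitment is remote and no staff member is present, so nobody would notice silent playback.

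**Working it through.** The plan gives no power, effect size, SD, significance level or dropout rate, and the sample size is set by budget (6.7). There is therefore no figure of the plan's own to reproduce, and what follows is illustrative.

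**Inputs from the documents.** N = 750 (6.1); seven groups, six voiced and one text (6.1, 6.7); pairwise two-sample comparisons (6.7).

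**Assumed inputs.** Equal allocation, since no ratio is stated; SD = 1; two-sided 5%; true difference d = 0.30 SD; share without sound f = 5%, 10% or 20%, equal across the voiced groups.

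**Group size.** 750/7 = 107.1, so about 107 per group. Pooled over the introduction factor, 2 × 107 = 214 per dialect level.

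**If non-hearers stay.** Dialect moves the score of the share (1-f) by d and of the share f by zero, so the observed difference is d × (1-f). The information about the contrast is multiplied by (1-f)², and the sample needed to keep the same power by 1/(1-f)². Power is from the two-sample t-test at the observed difference.

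| f | Observed difference, 0.30 × (1-f) | Information kept, (1-f)² | Sample factor, 1/(1-f)² | Power, 107 per group | Power, 214 per dialect level |
|---|---|---|---|---|---|
| 0 | 0.300 | 1.00 | 1.00 | 59% | 87% |
| 5% | 0.285 | 0.90 | 1.11 | 55% | 84% |
| 10% | 0.270 | 0.81 | 1.23 | 50% | 80% |
| 20% | 0.240 | 0.64 | 1.56 | 42% | 70% |

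The 107 column matches the pairwise comparisons that 6.7 plans. The 214 column needs pooling over the introduction factor, which 6.7 does not describe.

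**If non-hearers leave.** Each voiced group falls to 107 × (1-f), about 102, 96 or 86, while the text group stays at about 107. If leavers would have scored differently from stayers by an amount D, the mean of the stayers differs from the mean of everyone allocated by f × D. With D = 0.5 SD (assumed), the bias in voiced versus text is 0.05 × 0.5 = 0.025, 0.10 × 0.5 = 0.05 or 0.20 × 0.5 = 0.10 SD. Among the voiced groups the same shift occurs in each and cancels, provided audio failure is unrelated to dialect.

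Any one person either stays or leaves, so the two sets of figures are alternatives for a given f and must not be added.

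**The case against.** **A check may exist elsewhere.** The inclusion sentence in 6.1 is plainly not the full screener: it omits adherence to screening guidelines, although the Abstract recruits 375 adherent and 375 non-adherent patients. Section 6.8 also leaves the final presentation of the stimuli to focus-group feedback, and the survey instrument is not among the documents. This stands. A reader might infer that no check will take place; the documents support only that none is described.

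**Later exclusion can be valid.** A reader might infer that only a check before randomisation avoids bias. That goes too far. The SAE, low-AAE and high-AAE groups all need sound equally, so a later exclusion on a dialect-neutral record of playback could leave those contrasts comparable. It would not serve voiced versus text, because the text group never shows whether its sound works.

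**The size is unknown.** The documents give neither f nor an effect size nor an allocation ratio, and nothing in them shows how people without sound would behave. A reader might infer that the dialect effects are certainly diluted, or that the fall from 87% describes the planned tests. Neither is supported. Nor is all of the manipulation stated to be speech: 6.6 calls speech the primary manipulation.

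**It is an exploratory pilot.** No power target or decision rule is breached. That limits the severity. But 6.7 intends the results as preliminary estimates for future powered studies, and an attenuated estimate is not corrected by recruiting more people.

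**Conclusion.** The point holds in conditional form. As written, the plan allows people who cannot hear the recording to be randomised to a voiced group and to rate credibility, and it describes no means of identifying them. To the extent that they stay, dialect contrasts are multiplied by (1-f). To the extent that they leave, voiced versus text is open to selection, and contrasts among the voiced groups are little affected if audio failure is unrelated to dialect.

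Under the assumptions stated in the working, the planned pairwise comparison drops by about 4, 9 or 17 percentage points of power at f = 5%, 10% or 20%. These figures show scale only; they are not a forecast. The practical harm is that preliminary estimates passed to later studies may be too small. This is a cheap improvement worth making before data collection, not a flaw that invalidates the design.

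**What to change.** Add to 6.1 that, after consent and before randomisation, every participant, including those later allocated to text, completes a one-item audio check, for example hearing a short number sequence and entering it. Use a neutral stimulus and not a VHA voice, so that dialect is not primed. Those who fail are screened out and do not count toward the 750. Add to 6.7 that completion is reported by arm. If the survey instrument already contains such a check, the protocol need only state it and where it falls relative to randomisation.

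The cost is one survey item and a line or two of protocol text. The downsides are that some panel members are screened out and that the sample is limited to people with working sound. The item also shows only that sound worked at entry, not that the whole VHA message was heard.
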